#### 7.2.2.1. Management of hand foot skin reaction (HFSR)

Because HFSR has been reported for encorafenib, it is recommended that patients are educated prior to starting study treatment to avoid activities that can cause friction on hands and feet. In addition, supportive measures for prevention and/or management of HFSR should be instituted. Clinical judgment and experience of the treating physician should guide the management plan of each patient.

Dose reduction/interruption/discontinuation decisions for HFSR should be based on the CTCAE grade of the toxicity (Section 6.4) and the guidelines provided in table 10. A visit at a podiatrist may also be recommended at the discretion of the investigator.

# 7.2.2.2. Follow up evaluations for appearance of keratoacanthoma (KA) and/or squamous cell carcinoma (SCC)

The skin of patients will be examined regularly to monitor for the possible development of KA and/or SCC, as these have been reported to occur under selective BRAF inhibitor treatment (Flaherty et al 2010; Kefford et al 2010; Robert et al 2011). Patients should be instructed to inform their physicians upon the occurrence of any skin changes. In case of occurrence of KA and/or SCC, treatment of these lesions will follow institutional standards.

# 7.2.2.3. Management of nausea and/or vomiting

Because nausea and vomiting have been reported for encorafenib and binimetinib, it is recommended that patients are educated on the possibility of occurrence of these side effects prior to starting study treatment. Patient education as well as proper management of nausea and/or vomiting at the first sign is important. Clinical judgment and experience of the treating physician should guide the management plan of each patient. Patients experiencing nausea and/or vomiting CTCAE ≥1 will receive antiemetics at the discretion of the treating physician (as per local guideline). It is recommended that patients be provided a prescription for antiemetics and are instructed on the use of antiemetics on the first day of study drug treatment. Prophylactic antiemetics such as dexamethasone 8 mg, prochlorperazine, or metoclopramide may be administered to patients on an "as needed" basis.

Dose interruption/reduction decisions for nausea and/or vomiting should be based on the CTCAE grade of the toxicity and the guidelines provided in table 10.

As a guidance for recommendations on supportive measures for the prevention and/or management of nausea and/or vomiting, the published recommendation from American Society of Clinical Oncology (ASCO) , the European society of Medical Oncology (ESMO) and Multinational Association of supportive Care (MASCC)  can be used.

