#### 7.3. Concomitant Medications

All concomitant medications taken by the subject during the trial, starting from the date of signature of informed consent, will be recorded. The indication, dose, frequency, and dates of treatment will be recorded in the patient's medical records and in the appropriate section of the eCRF.

All medications (prescriptions or over-the-counter medications) on-going at the start of the trial or started during the study or until 30 days from the end of the last protocol treatment and different from the study medication will be documented.

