#### 6. OTHER ANALYSIS

#### 6.1. Dose analysis

In this section, we analyzed the pattern of Corticosteroids dosage between Assessment 1 and 2 with the aim of observing any changes in Corticosteroids usage during the second tumor assessment. To achieve this, we focused on the active Corticosteroids treatments administered during the initial and follow-up tumor assessments. Therefore, we included only those patients who had at least

one active Corticosteroids treatment during either the first or second tumor assessment.

Table 132: Frequency of Dose in Patients with Corticosteroid Treatment by Assessment

case			
CortiDose			
N			
Mean (95%CI)			
SD			
Median (95%CI)			
Range			

Table 133: Frequencies of Corticosteroid Dose Changes between Assessment 1 and 2

Overall
Dose comparison between Assessment 1 and 2 for each patient
Decreased Dose
Increased Dose
Maintained Dose

Table 134: Dose distribution according Assessment

Dose			
Mean (SD)			
Range			

1. Paired samples t-test

Table 135: Mean Difference in Change between Assessment 1 and Assessment 2

Overall
Dose difference between Assessment 1 and
2
N
Mean (95%CI)
SD
Median (95%CI)
Range

Figure 17: Trends in Assessment Differences

Table 136: List of all analyzed patients with their respective tumor assessment information and ongoing corticosteroid treatment. This includes both treatment and specific tumor assessment information

\*The dose scale (mg) on the vertical axis has been plotted on a logarithmic scale to show trends more clearly.

		Cort		Carti Carti	TumA	TumAs	TumAs	TumA	TumAs	TumA	Evillat Accoc A	ccoccm
Patient	CortiMedication Name	Corti :	CortiStar	Corti Corti	ssmT	smNon	smNon	ssmT s	smNon	ssmN	EVIIIILASSES A	133633111
Number	Name	Dose IUNI	tDate	Stop Ung	argSu	TargLe	TarqSu	argRe	TarqRe	ewLe	rcransment	ent 2
		ts		Date oing	m	sNA	m	en	sp	e	Resp 1 date	date
					1111	3117	1111	οp	эp	 		

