## 7. OTHER ANALYSES REQUIRED BY THE COORDINATOR

Group A: Symptomatic patients (Those belonging tp symptomatic cohort 2).

Group B: Asymptomatic patients, both those who were not treated with corticosteroids or anticonvulsants and those who were treated without association with brain metastases.

Group C: Patients who were asymptomatic at the time of study treatment but had been treated with corticosteroids in the days before due to a symptom of the disease.

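### SAP 6.1 pools all active corticosteroids whatever their indication, so antiemetic dexamethasone allowed by protocol section 7.2.2.3 could be read as a change in steroid use between tumour assessments

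*Combined protocol and SAP*

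**What the plan says.** Protocol section 7.2.2.3 covers nausea and vomiting under the study drugs: "It is recommended that patients be provided a prescription for antiemetics and are instructed on the use of antiemetics on the first day" of study treatment. It then says "Prophylactic antiemetics such as dexamethasone 8 mg, prochlorperazine, or metoclopramide may be administered to patients", as needed. No subgroup is singled out, so dexamethasone 8 mg is one of three named options open to any patient.

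SAP 6.1 (Dose analysis, within the section on other analyses) examines corticosteroid dose between assessments 1 and 2, "with the aim of observing any changes in Corticosteroids usage during the second tumor assessment". On the drugs counted, it says "we focused on the active Corticosteroids treatments administered during the initial and follow-up tumor assessments". On the patients counted, it requires at least "one active Corticosteroids treatment during either the first or second tumor assessment". Table 132 gives dose by assessment. Table 133, titled "Dose comparison between Assessment 1 and 2 for each patient", sorts patients into decreased, increased or maintained. Table 134 adds a paired t-test, and Table 135 gives the mean difference. Table 136 lists drug name, dose, units, start and stop dates and an ongoing flag beside lesion sums, new lesions and intracranial response. Indication appears in neither the text nor the table shells.

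The indication is collected. Protocol section 7.3 says of concomitant drugs: "The indication, dose, frequency, and dates of treatment will be recorded" in the medical records and the eCRF, and the concomitant-medication entry in section 8.1 repeats this. SAP section 7 uses the distinction once: its asymptomatic Group B includes "those who were treated without association with brain metastases", while Group C had steroids shortly before study treatment for a symptom of the disease.

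**The concern.** In a brain-metastasis trial, a table of steroid dose at successive tumour assessments, listed beside intracranial response, invites one reading: a falling dose means better control of the brain disease, a rising dose means worse. Treating drug-induced nausea with dexamethasone is a different matter, but under SAP 6.1 it enters the same dose variable. It can also bring in patients who never had a steroid for brain disease.

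At stake is the interpretation of Tables 132-135. A patient whose only steroid is an antiemetic course active at assessment 2 could be placed in the increased category. Inclusion criterion 12 of the protocol allows steroids only if the dose is not rising once the patient is in the trial, so such an entry might even be mistaken for loss of neurological control or a deviation. Because Table 136 omits indication, a reader could not sort this out from the listing. The problem is separate from adding different steroids in raw milligrams, since it arises even if every patient takes dexamethasone.

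**Working it through.** The plan states no figure to reproduce here. The check has two parts: a comparison of the texts, and an illustration of size on assumed data.

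**Comparison of the texts**

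1. Can an antiemetic steroid occur? Yes. Section 7.2.2.3 names dexamethasone 8 mg and limits it to no subgroup.
2. Would SAP 6.1 exclude it? No. The rules for drugs and for patients ask only whether a corticosteroid is active at an assessment.
3. Does another section supply a filter? None was found in the eligibility criteria, protocol sections 7.3 and 8.1, the baseline steroid tables (SAP Tables 29-30) or SAP section 7. Section 7 uses indication only to define Groups B and C.
4. Could a filter be applied? Yes, because indication is an eCRF item.

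So a record meets the SAP 6.1 rule if it is active at either assessment, whatever it was given for.

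**Illustration of size**

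From the documents: an antiemetic dose of 8 mg (section 7.2.2.3). Assumed, because the documents give no data: n patients who taper dexamethasone for brain metastases by 2 mg each; k patients whose only steroid is 8 mg antiemetic dexamethasone, active at assessment 2; and a steroid-free assessment entered as 0 mg.

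Mean change = (n × (-2) + k × 8) / (n + k). Share increased = k / (n + k).

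| k | n = 10: mean change (mg) | n = 10: increased | n = 20: mean change (mg) | n = 20: increased |
|---|---|---|---|---|
| 0 | -20/10 = -2.0 | 0% | -40/20 = -2.0 | 0% |
| 1 | -12/11 = -1.09 | 9.1% | -32/21 = -1.52 | 4.8% |
| 2 | -4/12 = -0.33 | 16.7% | -24/22 = -1.09 | 9.1% |
| 3 | 4/13 = +0.31 | 23.1% | -16/23 = -0.70 | 13.0% |
| 5 | 20/15 = +1.33 | 33.3% | 0/25 = 0.0 | 20.0% |

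Two variants with n = 10:

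- Antiemetic active only at assessment 1, k = 3: (-20 - 24)/13 = -3.38 mg, which exaggerates the taper.
- Antiemetic active at both assessments, k = 5: the share decreased falls from 10/10 = 100% to 10/15 = 67%.

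**Sensitivity to the assumptions**

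- *Entry of 0 mg.* If only patients with a recorded dose at both assessments are paired, those with an antiemetic at one assessment drop out of the paired comparison and its mean change stays at -2.0 mg.
- *Timing of assessment 1.* Both variants need assessment 1 to fall on treatment. SAP 6.1 calls the two time points initial and follow-up without defining them. SAP 6.2 lists baseline separately from assessments 1 and 2, which points to on-treatment. If the initial assessment is baseline, nausea from study drug cannot affect it, and this source of distortion can act only at assessment 2.

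**The case against.** The strongest reply is that SAP 6.1 does what it announces. Its stated aim is change in corticosteroid use, not in steroids given for brain disease, and counting every active steroid fits that aim. If the interest is steroid exposure at the time of the MRI, indication is irrelevant, and a table limited to brain-metastasis steroids would hide real exposure. This stands, and it is why the all-steroid summary should stay. It does not remove the ambiguity, because the same tables cannot tell a reader whether brain-disease steroids were tapered.

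A second reply is that the protocol only permits this use. Dexamethasone is one of three examples, is given as needed, and matters only if the course is recorded as active at an assessment. This also stands. A reader might infer that all patients receive dexamethasone, or that nausea treatment is certain to appear as a steroid change. The documents support neither, and they give no frequency.

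Third, a reader might take SAP 6.1 to be the only steroid analysis that ignores indication. It is not: the baseline Tables 29-30 report steroid use, type and stable or decreasing administration without it. Groups B and C are also a limited precedent, because they classify steroids given at or before the start of study treatment, not those started later.

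Finally, steroid dose change is neither a primary nor a secondary objective, and a breakdown can be added later from data already held. Both facts bear on severity. They do not show that the tables are interpretable as planned.

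**Conclusion.** The point holds as a possibility built into the plan. Following SAP 6.1 as written, an antiemetic dexamethasone course recorded as active at an assessment would be pooled with steroids given for brain disease and could be read as a change in steroid use alongside intracranial response.

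How often this happens cannot be determined from the documents. The illustration shows only that a few such records could cancel or reverse an apparent taper in a small analysed set. It rests on assumed patient numbers, on as-needed use being recorded as an 8 mg dose at the assessment, and on 0 mg being entered where no steroid is active. The sign reversal should not be quoted as an expected result.

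A reader might also infer that trial efficacy is affected. It is not: the effect is confined to a descriptive supplementary analysis with one paired t-test, and iORR, iPFS, OS and the success criterion do not use it. This is a cheap improvement of low severity.

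**What to change.** In SAP 6.1:

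- Keep the summary over all corticosteroids.
- Add to Tables 132-135 a breakdown by recorded indication: brain metastases or their symptoms, versus antiemetic or other.
- Base any statement about steroid tapering for brain disease on the first stratum alone.
- Add an indication column to Table 136.

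The indication is already collected, so no new data are needed and the breakdown can be run on the existing database. The cost is a little extra analysis work and small strata, which favours counts and listings over further testing. Nothing here implies a change to the antiemetic guidance in section 7.2.2.3.

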# 7.2.2.4 Monitoring of blood pressure

All patients must monitor their blood pressure at home at Days 14 and 42 after randomization if they meet at least one of the following criteria:

- Patients with history of hypertension and/or
- Patients receiving antihypertensive drugs before onset of study treatment and/or
- Patients with a screening systolic blood pressure of ≥140 mmHg and/or
- Patients with a screening diastolic blood pressure of ≥90 mmHg.

The investigator is to educate the patient on the signs and symptoms of hypertension and to evaluate the tension after taking any hypertensive drug and resting for 5 minutes in a sitting position if they use a home blood pressure monitor. More frequent assessments during the study drug treatment period may also be performed at the discretion of the investigator and if medically indicated.

Measurements are to be taken at the same time in the morning on Study Days 14 and 42, after taking any hypertensive medications and after being at rest for 5 minutes in a sitting position. If SBP  $\geq$ 160 mmHg, or DBP  $\geq$  100 mmHg, the patient should contact his/her investigator to have an unscheduled visit. At this unscheduled visit, the patient's blood pressure should be assessed, and these measurements must be documented in the eCRF page. Early initiation of treatment and aggressive management of emergent hypertension must be implemented after its diagnosis.

A diary will be provided for the patients to record their self-assessed blood pressure measurements and present the collected data to the investigator for evaluation and appropriate management. This diary must be maintained in the patient's source documentation.

#### 7.3. Concomitant Medications

All concomitant medications taken by the subject during the trial, starting from the date of signature of informed consent, will be recorded. The indication, dose, frequency, and dates of treatment will be recorded in the patient's medical records and in the appropriate section of the eCRF.

All medications (prescriptions or over-the-counter medications) on-going at the start of the trial or started during the study or until 30 days from the end of the last protocol treatment and different from the study medication will be documented.

#### 7.3.1. Permitted concomitant treatment

The patient must notify the investigational site about any new medications he/she takes after the start of the study drug. All medications (other than study drug) and significant non-drug therapies (including physical therapy, herbal/natural medications and blood transfusions) administered during the study must be listed on the Concomitant Medications or the Surgical and Medical Procedures eCRF. Patients taking concomitant medications chronically should maintain the same dose and dose schedule throughout the study if medically feasible.

Any medications that are considered necessary to protect subject welfare and will not interfere with the trial medication may be given at the Investigator's discretion.

Rescue medications may be administered to address anticipated adverse reactions or anticipated emergency situations.

#### 7.3.2. Permitted concomitant therapy requiring caution and/or action

Encorafenib is a reversible inhibitor of CYP2B6, CYP2C9, CYP3A4 and UGT1A1. It is also a time dependent inhibitor of CYP3A4. Binimetinib is also a reversible inhibitor of CYP2B6. Permitted medications to be used with caution in this study include those that are sensitive substrates of CYP2B6, CYP2C9, CYP3A4, and UGT1A1 or those substrates that have a narrow therapeutic index (NTI). Substrates of CYP3A4 are allowed based on a lack of interaction with midazolam. There is a potential for encorafenib to induce CYP3A4 at concentrations >10-50 uM, which may reduce the effectiveness of hormonal contraception methods. Therefore, the use of at least one form of non-hormonal contraception will be needed during the participation in this study. Please see Section 6.2 exclusion criterion 18 for use of contraception methods required for this study. Caution should be used in patients receiving concomitant treatment with other drugs that are substrates of CYP3A4 as the efficacy of these drugs could be reduced when administered with encorafenib.

Encorafenib has been identified to be primarily metabolized by CYP3A4 and to a lesser extent by CYP2C19 in vitro. The use of strong inhibitors of CYP3A4 are prohibited, please see section below. Moderate inhibitors of CYP3A4 and strong inhibitors of CYP2C19 should be taken with caution when co-administered with encorafenib. Patients should be closely monitored for the occurrence of adverse events. Regular assessments will be performed as described in Table 11. If a patient develops a toxicity, encorafenib dose may be adjusted as outlined in the dose modification Table 8.

Binimetinib has been identified to be primarily metabolized by glucuronidation. It is advised that strong inhibitors of UGT1A1 should be taken with caution when co-administered with binimetinib. Patients should be closely monitored for the occurrence of adverse events. Regular assessments will be performed as described in Table 11. If a patient develops a toxicity, binimetinib dose may be adjusted as outlined in the dose modification Table 9. In vitro data showed that both binimetinib and encorafenib are substrates of P-gp. Binimetinib is also a substrate of BCRP. Thus, the use of drugs that are known to inhibit or induce P-gp and BCRP should be used with caution. Encorafenib is a BCRP inhibitor. It is also a potent inhibitor of the renal transporters OAT1, OAT3 and OCT2 and the hepatic transporters OATP1B1 and OATP1B3. Therefore, the co-administration of drugs that are known to be sensitive or NTI substrate of BCRP, OAT1, OAT3, OCT2, OATP1B1 and OATP1B3 should be used with caution.

The solubility of binimetinib and encorafenib is pH dependent and a 10-fold decrease in solubility is observed between pH 1 and 2. Patients receiving concomitant treatments that could potentially modify the gastric pH (i.e. PPI) should be instructed to take them at least two hours after the administration of binimetinib.

#### 7.3.3. Prohibited concomitant treatment

Any other investigational treatment within the past 30 days of treatment initiation and during the trial is disallowed.

Anticancer therapies (including chemo- or biologic-therapy or radiation therapy, covering >30% of the red bone marrow reserve, and surgery) are prohibited while the patients are receiving study treatment. If such therapeutic measures are required for a patient, then the patient must be discontinued from study treatment. If local treatment, radiotherapy or surgery, is indicated by the protocol of this study, it is allowed but following the next indication regarding the study treatment. To reduce possible skin toxicity during and after radiotherapy, encorafenib and binimetinib will be interrupted 24h before radiotherapy and restart 24h after the last dose of radiotherapy.

The concomitant use of strong CYP3A4 inhibitors would likely significantly increase the exposure of encorafenib and thus should not be used during this study.

#### 7.4. Treatment Compliance

Study drug compliance will be assessed by the Investigator and/or study personnel at each patient visit for encorafenib and binimetinib and information provided by the patient and/or caregiver will be captured in the patient records as part of source documentation at each patient visit. Corresponding drug administration information will be reported also in the eCRF.

A patient medication diary will be provided for each patient. Patients or caregivers should complete this diary during the entire study.

The investigator or designee must maintain an accurate record of the shipment and dispensing of study treatments in the IWRS system designed for this trial (access to IWRS system will be created by study monitors during site initiation visit or can be asked by email to:

Patients will be asked to return all unused study treatment and packaging on a regular basis, at the end of the study or at the time of study treatment discontinuation.

Compliance with the IMP schema is critical for patients and trial outcomes, and any deviation from the IMP schema may jeopardize trial results or may affect patient safety; for these reasons, non-compliance may be considered as a protocol deviation. When an investigational product is dispensed in a clinical trial, the investigator or a person designated by the investigator will ensure high level of compliance with the investigational product administration procedures.

All stages from IMP since will be documented in the corresponding forms to guarantee traceability during the procedure.

For this trial, IMP compliance will be assessed by reviewing the consistency of information in the IWRS, the eCRF, patient records, nurse sheets, and in the pharmacy source documentation.

At study close-out, and, as appropriate during the study, the investigator will return all used and unused study treatment, packaging, drug labels to the Sponsor or designee's monitor or to the Sponsor address provided in the investigator folder at each site.

Upon approval from the Sponsor personnel and after accountability has been confirmed by the Sponsor or designee's monitor, the study drug supply can be destroyed by the clinical site, according their normal practise, or, when destruction in site is not possible, destroyed at Sponsor supply vendor, as appropriate.

